4.2 Secondary Endpoints

- Time from randomisation to start of next line of systemic therapy or clinical decision that patient not suitable for further systemic therapy as determined by the treating physician, or death.
- Overall survival time from randomisation until death from any cause

HALT Protocol

- Patterns of disease progression identified from CT scans / PET-CT scans taken at 3 monthly intervals to further document natural history of oncogene-addicted NSCLC
- Radiotherapy toxicities (acute and late) assessed using CTCAE v4.0 (clinician and patient versions where available). Acute events are defined as ≤ 90 days post SBRT start date (applicable for each subsequent course of SBRT where relevant) and late events are defined as > 90 days, both assessed using CTCAE v4.0.
- Quality of Life assessed using EQ-5D-5L and the EORTC QLQ-C30
- Measurement of resistant sub-clones in ctDNA measured at baseline, post-randomisation and upon progression.
- Time to failure of next line treatment time from randomisation to switch from next line of active systemic therapy.

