	tumour-specific oncological intervention (e.g. change in					
	systemic therapy or localised non-SBRT radiotherapy) as					
	determined by the treating physician					
PRIMARY ENDPOINT	New or existing intra-cranial lesions not amenable to radical					
	surgery or SRS					
	• Development of new extra-cranial lesions or progression of					
	existing extra-cranial lesions not meeting the criteria for					
	SBRT treatment (e.g. size > 7cm)					
	 Development of >5 new or progressing extra-cranial lesions 					
	at any one point in time (i.e. widespread progression)					
	• Time to change in systemic therapy or clinical decision that					
	patient not suitable for further systemic therapy					
	Overall survival					
	 Patterns of disease progression 					
SECONDARY ENDPOINTS	 Radiotherapy toxicities (acute and late) using CTCAE 					
	Quality of Life					
	 Time to failure of next line of systemic therapy 					
	Measurement of resistant sub-clones in ctDNA					
	Deep sequencing analysis will be used to model tumour					
EXPLORATORY ENDPOINTS	evolution, neo-antigen burden and genomic instability in					
	paired tumour tissue at OPD baseline and at the time of					

	further progression (where available) in addition to ctDNA
	samples.
	 Where PET imaging has been undertaken (as per standard
	site practice), assessment of PET findings in relation to
	clinical outcome.
	All patients will be assessed 8 weeks post randomisation.
	Subsequent follow-up visits will be aligned with routine care and
FOLLOW UP	will occur at 3 monthly intervals from the end of treatment
	assessment visit.

HALT TRIAL SCHEMA

Follow-Up: All patients will be seen at 8 weeks post randomisation then every 3 months thereafter with tumour imaging and toxicity assessment occurring at each 3 monthly follow up visit until disease progression. QoL will be assessed at baseline, 8 weeks and at the first follow up visit. Patients will continue to be followed until death with information on current treatment and status being recorded at routine practice assessments.

Sample Collection: Blood samples will be collected from patients at baseline, after the first SBRT fraction (treatment group only), 8 weeks, 5 months and 8 months post-randomisation and upon progression. Archival tissue will be requested from all patients where available. Voluntary biopsies of progressive lesions will also be requested where possible.

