2.2 Secondary Objectives

The secondary trial objectives are to assess:

- Time to change in systemic therapy
- Overall survival (planned phase III primary endpoint)
- Patterns of disease progression
- Clinician and patient reported acute and late toxicity (CTCAE v4.0)
- Quality of life
- Clearance of detectable resistant sub-clones measurable in ctDNA in SBRT arm
- Time to failure of next line treatment

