4 STUDY ENDPOINTS

4.1 Primary Endpoint

Progression free survival defined as the time from randomisation to the first of one of the following events or death from any cause:

- Clinically symptomatic progression requiring palliative tumour-specific oncological intervention (e.g. change in systemic therapy or localised non-SBRT radiotherapy) as determined by the treating physician.
 - New or existing intra-cranial lesions not amenable to radical surgery or SRS.
- Development of new extra-cranial lesions or progression of existing extra-cranial lesions not meeting the criteria for SBRT treatment (e.g. size >7cm)
- Development of >5 new or progressing extra-cranial lesion at any one point in time (i.e. widespread progression)

Progression will be assessed radiologically at each clinic visit following randomisation or more frequently if clinically indicated. The scans at time of trial entry will be used as the baseline for assessment. Determining progression of new or existing extra-cranial OP lesions, as stated above, will

be by assessment of % change of individual lesions compared to the baseline scan, with progression defined as a \geq 20% change from baseline in an individual lesion. In these instances, the criteria for determining progression meeting the primary endpoint definition will be based on an assessment of SBRT suitability as defined below. This method will be used to determine OPD in both the control and SBRT treatment groups to minimise bias in determining PFS events. The HALT virtual MDT should review progression events in both groups and research teams at participating centres will be required to upload the scans indicating further progressive disease for review.

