It is estimated that up to 20% of patients will be registered and found not to be eligible. In order for 110 patients to be randomised it is estimated that 138 patients will need to be registered. Data to base these estimates on is limited and therefore the Independent Data Monitoring Committee (IDMC) and Trial Management Group (TMG) will review the number of patients registered during the trial.

Phase III trial: an average median overall survival of 12 months (mutation types combined) in the control group is anticipated at this stage. The number of patients required for the phase III trial will be influenced considerably by the designated magnitude of minimum clinically important difference and this estimate will be refined after the phase II trial. Using the log rank method as above and assuming a 5-year recruitment period, a total of 272-875 patients (power 80%, alpha 5%) would be required to detect a 6 month or 3 month improvement in overall survival with SBRT (12 to 18 month and 12 to 15 month improvement respectively) and it is anticipated that the designated number of patients

required will lie within this range. It is envisaged that patients recruited to the phase II component will also contribute to the phase III endpoint given the rare population and the integrated design. Assumptions made about the phase III trial design and sample size will be re-assessed for relevance and suitability during the transition phase (Appendix 1). Should the target sample size for phase III be at the lower end of the range recruitment is likely to be completed more quickly.

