13.3 Statistical Analysis Plan

Analyses of efficacy will be according to the intention to treat principle. Time to event endpoints will be presented using Kaplan Meier survival plots and compared between treatment groups using the log-rank test. Hazard ratios will be derived from Cox proportional hazards models or methods such as restricted mean survival should the assumption of proportionality not be met. A planned subgroup analysis will explore treatment effect by mutation status (e.g. EGFR+ vs. other mutation), however it is recognised there is limited power to estimate these subgroup effects and thus analyses will be interpreted with the appropriate caution.

Patterns of further disease progression will be summarised by treatment group to document the natural history of oncogene-addicted lung disease.

Acute and late toxicity related to SBRT treatment, both physician and patient reported, will be analysed separately and summarised as frequencies and percentages at each time point with adjustment made for multiple testing. The proportion experiencing toxicity of any grade and grade \geq 3 will be presented and any comparisons made between randomised treatment groups using Fisher's exact tests. All safety analyses will use a safety population which will be pre-defined in the Statistical Analysis Plan.

Quality of life (QoL) data will be analysed using standard algorithms to derive scores and handle missing data according to the chosen questionnaire's scoring manual. Descriptive statistics (median, IQR, range) will be presented by treatment group at each timepoint. Analyses to account for the longitudinal nature of the data may also be used.

The integral translational work will include assessment of ctDNA clearance as a binary outcome with comparison between randomised treatment groups made using Fisher's exact tests. Logistic regression models will be used to adjust for any relevant baseline characteristics. Exploratory analyses

will look at the genetic relationship between baseline circulating biomarkers and archival tumour samples.

Further details of analysis methods will be specified in a Statistical Analysis Plan in accordance with ICR-CTSU Standard Operating Procedures.

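### Time to failure of next-line treatment counts only a switch of therapy as an event, so deaths and decisions against further therapy drop out and the estimated time to failure is too long

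*Protocol*

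**What the plan says.** Section 4.2 gives the last secondary endpoint as "Time to failure of next line treatment time from randomisation to switch from next line of active systemic therapy". The secondary objectives (section 2.2) and the trial summary only name it, as "Time to failure of next line treatment" and "Time to failure of next line of systemic therapy". Neither adds an event.

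The first endpoint in the same list, time to the start of the next systemic therapy, also ends at a "clinical decision that patient not suitable for further systemic therapy as determined by the treating physician, or death". The primary endpoint in section 4.1 runs to "the first of one of the following events or death from any cause".

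On analysis, section 13.3 says: "Time to event endpoints will be presented using Kaplan Meier survival plots and compared between treatment groups using the log-rank test". It names no competing-risk method. The protocol states no separate censoring rule for this endpoint and leaves further detail to the statistical analysis plan.

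**The concern.** A patient whose next-line treatment ends in death, or who is judged unfit for anything more, has failed that line in the most serious way. Under the section 4.2 wording that patient has no event. Someone who dies before starting a next line can never have one.

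This produces an odd ordering. Such a patient counts as failed on time to next systemic therapy but as event-free on time to failure of the line after it, although failure of the later line cannot sensibly be still pending once the patient has died.

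These patients are unlikely to be few. The endpoint spans two lines of treatment from randomisation, and for phase III planning section 13.1 says "an average median overall survival of 12 months (mutation types combined) in the control group is anticipated at this stage". At stake are a secondary Kaplan-Meier curve that reads too favourably in absolute terms and a between-arm comparison that takes no account of deaths.

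**Working it through.** **Plan's own figure.** The protocol gives no expected value for this endpoint, so there is nothing to reproduce directly. As a check on the design, the Schoenfeld formula with a hazard ratio of 0.5, 5% two-sided alpha, 90% power and 2:1 allocation gives 98.4 events (99 rounded up). Section 13.1 states 97, at which power is 89.6%. The PFS calculation reproduces closely and does not depend on this point.

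**How each outcome is handled, as written**

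| Outcome | Time to next systemic therapy | Time to failure of next line |
|---|---|---|
| Death before a next line starts | event | no event |
| Death during the next line | already had an event | no event |
| Judged unsuitable for more systemic therapy | event | no event |
| Stops next line, no further drug | already had an event | no event on the plain reading |
| Switches from the next line | already had an event | event |

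**Direction for the curve.** At each switch time, death-censored Kaplan-Meier multiplies by one minus switches over number at risk. At death times it does not drop at all. A curve that counted death would drop there too. The switch-only curve therefore lies on or above it.

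**Size under constant hazards.** Let h_s be the hazard of a switch and h_o the hazard of any other failure.

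- Switch-only median = ln 2 / h_s
- Median counting all failures = ln 2 / (h_s + h_o)
- Ratio = (h_s + h_o) / h_s = 1 / (1 - q), with q = h_o / (h_s + h_o)

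The protocol gives no q. As assumptions:

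| q | Factor 1/(1-q) |
|---|---|
| 0.2 | 1.25 |
| 0.3 | 1.43 |
| 0.4 | 1.67 |
| 0.5 | 2.0 |

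A second illustration works from assumed medians. Take a switch-only median of 12 months and a median time to death without a switch of 12, 18, 24 or 36 months. The median counting both is 6.0, 7.2, 8.0 or 9.0 months, so the overstatement is 2.0, 1.67, 1.5 or 1.33. Letting the switch median vary from 9 to 15 months widens the range to 1.25 to 2.25.

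**Between-arm comparison.** Take control-arm medians of 12 months for a switch and 24 months for death without a switch (both assumed). The hazards are then in the ratio 2:1, and the hazard ratio (HR) for switch or death is (2 × HR_switch + HR_death) / 3.

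| HR, switch only | HR, death without switch | HR, switch or death |
|---|---|---|
| 0.70 | 0.7 | 0.70 |
| 0.70 | 1.0 | 0.80 |
| 0.70 | 1.3 | 0.90 |
| 1.0 | 0.67 | 0.89 |

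In the second and third rows the switch-only analysis flatters SBRT. In the fourth it hides a benefit. In the first it makes no difference. If deaths replace switches rather than adding to them, the result can also mislead under a true null: with equal total failure hazards and q of 0.5 in one arm against 0.3 in the other, the apparent hazard ratio is 0.5/0.7 = 0.71 when the true ratio is 1.0.

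**The case against.** **The protocol does not say these patients are censored.** True. That follows from combining a switch-only event with the section 13.3 methods. A statistical analysis plan could keep the switch as the event and treat death as a competing event without contradicting section 4.2. It could not count death as a failure without departing from the protocol's definition. The point stands as a badly fixed event, not as a missing detail.

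**Switching from a line could be read as leaving it.** This is possible, and it would bring in patients who stop without another drug. It cannot bring in death.

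**The stakes are limited.** This is the last-listed secondary endpoint and no power is attached to it. PFS, time to next systemic therapy and overall survival all count death, so excess mortality would show elsewhere. That limits the consequence but does not correct this curve.

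**Stronger readings that the protocol does not support.**

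- A reader might infer that an arm with more early deaths must appear to do better. Under constant hazards, extra deaths leave the switch-only curve unchanged. They lengthen it only if they replace switches.
- A reader might infer that the reported median would exceed the 12-month survival figure. That depends on the assumed inputs: an all-failure median of 8 months with q of 0.3 gives 8/0.7 = 11.4 months. The 12 months is also a provisional control-group figure for phase III.
- A reader might suppose the endpoint exists to show whether delaying a drug switch harms later treatment. The protocol states no such purpose.

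**Conclusion.** The point holds for the event definition. Section 4.2 leaves out death and decisions against further therapy and, on the plain reading, stopping without another drug. This is inconsistent with the first secondary endpoint in the same list. Analysed by Kaplan-Meier as section 13.3 provides, the estimated time to failure is too long.

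The direction for the curve follows from the definition. The size rests on assumed values of q and on constant hazards, and should be quoted only as a range: 1.25 to 2.0 for q from 0.2 to 0.5. The bias in the treatment comparison has no fixed sign. What can be said is that an excess of deaths in either arm would not register as failure on this endpoint. The primary endpoint, sample size and alpha are not affected.

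**What to change.** Amend section 4.2 so that the endpoint runs from randomisation to the earliest of:

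- switching or permanently stopping the next line;
- a clinical decision that no further systemic therapy is suitable;
- death from any cause, including before any next line starts.

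Censor only patients who are alive and have not failed at last contact.

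If the sponsor prefers to keep the switch as the only event, state that death and stopping without a further line are competing events. Report cumulative incidence, and do not describe the result as time to failure without that qualification.

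The cost is one sentence in the protocol and matching wording in the statistical analysis plan. Section 10.4 already has patient status and current treatment recorded until death, so no new data collection is needed.

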4.3 Exploratory Endpoints

- Deep sequencing analysis will be used to model tumour evolution, neo-antigen burden and genomic instability in paired tumour tissue at OPD baseline and at the time of further progression (where available) in addition to ctDNA samples.
- Where PET imaging has been undertaken (as per standard site practice), assessment of PET findings in relation to clinical outcome.

5 PATIENT SELECTION & ELIGIBILITY

5.1 Number of Participants

The aim is to randomise 110 participants for the phase II component of the trial; anticipated to be 73 patients randomised to the treatment group (SBRT treatment), 37 randomised to the control group (no SBRT treatment). It is estimated that 138 patients will need to be registered in order for 110 patients to be randomised.

5.2 Source of Participants

Participants will be recruited from approximately 20 sites in the UK plus additional sites from participating countries within the EORTC network. Potential participants will be identified in oncology clinics and discussed at local Multi-Disciplinary Team (MDT) meetings.

5.3 Inclusion Criteria

- 1. Male or female, \geq 16 years of age
- 2. Established histological diagnosis of advanced NSCLC, not suitable for radical treatment, with defined actionable mutation receiving targeted TKI therapy
- 3. Radiologically confirmed response to TKI therapy (assessed locally usually 2-3 months post commencing TKI)
- 4. Confirmed OPD defined as ≤ 5 extracranial sites of progressive disease. All sites must be visible, imaging defined targets and suitable for treatment with SBRT as determined by the virtual MDT and in accordance with the HALT Radiotherapy planning and delivery guidance document.

- 5. Adequate baseline organ function to allow SBRT to all relevant targets
- 6. Predicted life expectancy \geq 6 months
- 7. Karnofsky Index \geq 60% and ECOG 0-2
- 8. Provision of written informed consent

5.4 Exclusion Criteria

- 1. > 5 extracranial sites of progressive disease
- 2. Progressing or newly diagnosed brain metastases identified at the time of trial entry, not amenable to radical surgery or SRS. Previously treated brain metastases (i.e. palliative radiotherapy or systemic therapy) which have remained clinically and radiologically stable for ≥ 6 months are permissible.
- 3. Prior radiotherapy near the oligoprogressive lesion precluding ablative SBRT. Suitability of lesions for ablative SBRT as part of the trial defined in section 4.1 of this document and will be determined by the HALT virtual MDT
- 4. Co-morbidities considered clinically precluding the safe use of SBRT (as detailed in the HALT radiotherapy planning and delivery guidelines).
- 5. Any psychological, sociological or geographical issue potentially hampering compliance with the study
- 6. Pregnancy

5.5 Life Style Guidelines

Participants randomised to receive SBRT must be surgically sterile or if female be post-menopausal, or must agree to use effective contraception during the period of therapy. Patients in the control group should continue to follow local guidelines for TKI therapy. Effective contraception is defined as double barrier contraception (e.g. condom plus spermicide in combination with a diaphragm, cervical cap or intrauterine device).

6 VIRTUAL MDT

A virtual MDT will be established as part of the HALT trial to provide consistent interpretation and central confirmation of patient eligibility, and where necessary assessment of progression events meeting the primary endpoint in both the control and treatment groups and assessment of progression in lesions treated with SBRT. The HALT virtual MDT will consist of clinical members of the HALT trial team in addition to at least one independent radiologist. As a minimum, 2 clinicians and 1 radiologist will be required for individual scan assessment.

It is intended that the Research PACS (XNAT) software system, housed and maintained at the Institute of Cancer Research, will be used to manage the required image upload and review process. Named individuals at each participating centre will be provided with access details to allow upload of the relevant anonymised patient scans and reports where available onto a secure server.

Where considered appropriate by the vMDT, centres having previously submitted \geq 3 patients for vMDT review where no issues in confirmation of oligoprogression or SBRT suitability have been identified, will be permitted to follow a streamlined radiology review. This would consist of full central

radiology review of the required patient scans, as with the usual virtual MDT process, with full review by the vMDT not considered necessary unless radiology identified specific issues for discussion. The decision to move to a streamlined review would be on a per centre basis following consensus approval by the vMDT.

6.1 Eligibility Assessment

Research teams at site will be required to upload imaging scans and reports relating to the following time points to enable assessment of eligibility:

- Scan informing decision to commence current line of TKI therapy
- Scan indicating best and/or initial response to current line of TKI therapy
- Scan prior to current OPD scan (if different from scan above)
- Scan identifying current oligoprogression

The virtual MDT will assess eligibility based on number of OPD sites and SBRT suitability of all OP lesions. An assessment of tumour burden will also be conducted for patients considered eligible. If patients have been previously treated for brain metastases, MRI and/or contrast CT brain scans may be requested to confirm stable disease \geq 6 months.

Criteria for PET-avid OPD lesions

Progression of new or existing OPD lesions can be diagnosed based on FDG avidity on PET-CT when there is no change in size/morphology of the lesion confirmed by CT. All patients where OPD is diagnosed by PET-CT should be discussed at a HALT virtual MDT.

OPD diagnosed on PET is defined as:

- a) A new lesion in which SUVmax is above background SUV when compared to the scan indicating best response to current line TKI. If no previous scan is available for comparison, further interval PET imaging should be considered or if the lesion is not easily visible on CT a diagnostic MRI should be considered to confirm OPD.
- b) OR increase in SUV max of \geq 30% and an absolute increase by 0.8 units compared to the nadir/previous scan as available.

Progression should continue to be assessed as described in section 4.1, defined as a \geq 20% change from baseline in an individual lesion. However, subsequent follow-up PET-CT scans can be used to evaluate any new OPD lesions suitable for repeat SBRT for those randomised to SBRT treatment.

